The Value of a High-Volume Image-Guided Injection in Chronic Midportion Achilles Tendinopathy: a Double-blind, Randomized, Placebo-controlled Clinical Trial

NCT02996409

13-8-2019

Statistical analysis plan HAT-study

The patients will be analyzed by intention-to-treat. To test for the effect of treatment on the between-group difference in primary outcome (VISA-A score), we will use the Generalized Estimation Equations (GEE) model. Adjustments will be made for the following baseline variables: age, sex, BMI and duration of symptoms. The same approach will be used for the following secondary outcomes: modified Öhberg score (0-4+ score), VAS score during 10-hop test, flexibility m. gastrocnemius, flexibility m. soleus, power m. gastrocnemius, power m. soleus.

Fisher's exact tests will be performed for the following secondary outcomes: Return to desired sport (categorized, we will dichotomize for: no return to sport and return to sport, not to desired sport combined as no return to sport; return to sport, not at pre-injury level and return to sport at pre-injury level combined as return to sport), patient satisfaction (categorized, we will dichotomize for: good/excellent as satisfied, moderate/poor as dissatisfied), and patient acceptable symptoms scale (PASS; categorized, symptoms acceptable/not acceptable).

Missing data will not be imputed, however sensitivity analyses will be performed if missing data is more than 5%. The researcher who will perform the analyses will be blinded to the allocated treatment. No interim analyses were planned for this study. Given the large amount of data derived from this trial, we intend to present the results in multiple papers.

Update 12-8-2019: We excluded the baseline VISA-A score as adjusted variable in the GEE-model, since adjustments are already being made as the baseline VISA-A score is included in the model as time point. Therefore, our biomedical statisticians stated that it was not necessary to adjust for this variable twice.

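### Does the 5% trigger for missing-data sensitivity analyses leave the planned results unprotected?

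*SAP*

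**What the plan says.** The SAP is one short section, headed Statistical analysis plan HAT-study, with three paragraphs and a dated update.

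- **Population (paragraph 1):** "The patients will be analyzed by intention-to-treat".
- **Repeated outcomes (paragraph 1):** VISA-A is analysed by GEE. For six further outcomes, "The same approach will be used for the following secondary outcomes". The update adds that "the baseline VISA-A score is included in the model as time point".
- **Binary outcomes (paragraph 2):** "Fisher's exact tests will be performed for the following secondary outcomes: Return to desired sport", followed by satisfaction and PASS. Each answer category is assigned to one side of a dichotomy, and an absent answer is assigned to neither.
- **Missing data (paragraph 3):** "Missing data will not be imputed, however sensitivity analyses will be performed if missing data is more than 5" per cent. The same paragraph says "The researcher who will perform the analyses will be blinded to the allocated treatment" and "we intend to present the results in multiple papers".

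The SAP gives no sample size, number of visits, event rate or expected dropout.

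**The concern.** Three things about the missing-data sentence look unsatisfactory.

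1. **The base.** The 5% could be counted per outcome, per visit, per arm or over all records. One trigger serves ten outcomes (seven by GEE, three by Fisher's test) that may appear in separate papers. If the base is chosen once the data are in, so is the decision to run the check.
2. **The content.** No sensitivity analysis is named. How fragile a result is depends on who is missing and how close the result is, and passing 5% settles neither.
3. **The binary outcomes.** Without imputation and without a rule for an absent answer, Fisher's test can use only patients with an observed outcome. That sits awkwardly beside intention-to-treat. At or below 5% nothing obliges anyone to look further.

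A smaller worry concerns VISA-A. GEE on unimputed data is not generally protected when dropout depends on earlier scores. At stake would be a claim on return to sport, satisfaction or PASS that turns on a few unseen patients.

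**Working it through.** The SAP has no figure to reproduce, because 5% is a rule and not a result. All inputs below except the 5% are assumptions.

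**Step 1: does the base matter?** Assume dropout of 2, 4, 6 and 8% over four follow-up visits.

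- Last visit: 8%, above the trigger.
- Follow-up records: (2 + 4 + 6 + 8)/4 = 5%, not above it.
- All records with baseline: (0 + 2 + 4 + 6 + 8)/5 = 4%, not above it.

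Pooling over outcomes has the same effect. Six outcomes at 7% and four at 2% give (6 × 7 + 4 × 2)/10 = 5.0%. In the extreme, if all missing values fall at one visit and 5% is pooled over V visits, that visit can lack 5% × V of patients: 15% for V = 3 and 30% for V = 6. The ambiguity is real.

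**Step 2: how far can 5% missing move a Fisher result?** Assume 40 per arm, 2 missing in each (5.0%, so not more than 5%) and a two-sided 0.05 level. The observed table 27/38 vs 17/38 gives p = 0.036. Let i and j be the successes among the missing in the first and second arm. The completed tables (27 + i)/40 vs (17 + j)/40 give:

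| | j = 0 | j = 1 | j = 2 |
|---|---|---|---|
| i = 0 | 0.042 | 0.071 | 0.113 |
| i = 1 | 0.024 | 0.041 | 0.069 |
| i = 2 | 0.012 | 0.022 | 0.039 |

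Three of the nine are not significant.

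**Step 3: how likely are those three?** They are not equally probable cells. Let missing patients succeed at their arm's observed rate, 27/38 = 0.711 and 17/38 = 0.447.

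- P(i = 0) = 0.289² = 0.084, and P(i = 1) = 2 × 0.711 × 0.289 = 0.411.
- P(j = 1) = 2 × 0.447 × 0.553 = 0.494, and P(j = 2) = 0.447² = 0.200.
- Total = 0.084 × (0.494 + 0.200) + 0.411 × 0.200 = 0.058 + 0.082 = 0.14.

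**Step 4: how wide is the fragile zone?** Hold 17/38 fixed.

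- 26/38: p = 0.063, not significant to begin with.
- 27/38: p = 0.036, the table in Step 2.
- 28/38: p = 0.019. Only i = 0, j = 2 reverses it (28/40 vs 19/40, p = 0.069), with probability (10/38)² × (17/38)² = 0.069 × 0.200 = 0.014.
- 29/38: p = 0.009. The worst completion (29/40 vs 19/40) gives p = 0.039, so nothing reverses it.

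Only two success counts are both significant and reversible. In points, the margin is (29 − 27)/38 = 5.3. The same calculation gives 3.4, 4.2 and 5.3 points for 30, 50 and 60 per arm with 1, 2 and 3 missing in each.

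**Step 5: what does the trigger control?** The no-imputation clause carries no threshold. The main Fisher tests therefore use observed patients at 3% missing and at 15% missing alike. Crossing 5% leaves every planned estimate and p-value unchanged and only adds a supplementary analysis.

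**Step 6: VISA-A.** A simulation had no true effect and about 5% of each arm missing at the last visit, with dropout on the previous score. Bias at that visit was at most 0.001 SD when dropout was equal and in the same direction in both arms. The largest value, 0.118 SD, needed an independence working correlation, opposite dropout directions in the two arms and a doubled dropout slope. An exchangeable working correlation gave at most 0.015 SD in the same settings. These are ranges over the settings run and not bounds. The SAP does not state the working correlation, and the protocol may.

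**The case for a change.** The best case for a change is that the fault lies in a rule this SAP fixes itself, so an unseen protocol does not excuse it. A trigger with no base can be read after the fact. Blinding to treatment does not prevent that, since a denominator can be chosen without knowing the arms. The p-values in the 40-per-arm example are correct, and a borderline table can be found at every arm size tried. With 2 missing in one arm only, 27/38 vs 18/40 gives p = 0.024, and 27/40 vs 18/40 gives p = 0.071 if both missing patients failed. The remedy would cost a sentence and some programming.

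Part of this stands: the base is undefined and the check unnamed, and a line on each would have been tidier. The rest carries less weight.

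- **The examples** are the smallest significant tables or extreme completions. They show that borderline p-values are borderline, not that the planned test is biased.
- **Blinding** removes the main motive for choosing a base, which is to favour an arm.
- **The reader's own check** needs only the observed counts and the numbers randomised.
- **The remedy** has costs of its own. Replacing the sentence outright would delete the rule that the main analyses are not imputed. A list of mandatory checks confined to VISA-A and the binary outcomes would leave the six secondary GEE outcomes without the check they now get above 5%. Counting missing as non-response can itself bias, and it misses the fragility in the 40-per-arm table (p = 0.042).

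**Conclusion.** No change is called for. The sentence is loosely written, but a plan followed as it stands is not shown to give a wrong result when 5% or less is missing. No planned estimate or test depends on how the 5% is counted. The fragile zone in the worked example is two success counts wide, with reversal probabilities of about 14% and 1.4%, and it concerns three secondary outcomes. The VISA-A bias at this level of missingness is small except under an extreme combination of assumptions.

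The gap is one that an analyst fills sensibly: count missing data for each outcome at each visit, which is the share that bears on the test being reported, and choose a check suited to that outcome. Whether several sensitivity analyses should be compulsory at any level of missingness is a matter on which experienced statisticians differ.

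This rests on assumed arm sizes of 30 to 60, success of about 45% in the comparison arm, and missing patients who succeed at their arm's observed rate. If missing patients differ sharply from observed ones, the 14% could be higher for that one table, but from 29/38 upward no completion reverses the result. The judgement also rests on the per-outcome, per-visit reading. A pooled count that hid 15 to 30% missing at one visit would be a poor reading of the rule, and the reported denominators would reveal it.

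### Having baseline VISA-A as a GEE time point does not by itself adjust for it, so the reason for dropping it as a covariate fails and the primary comparison may lose precision

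*SAP*

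**What the plan says.** The first paragraph of the SAP sets the primary analysis. For "the between-group difference in primary outcome (VISA-A score), we will use the Generalized Estimation Equations (GEE) model". On covariates it says: "Adjustments will be made for the following baseline variables: age, sex, BMI and duration of symptoms". Baseline VISA-A is not among them.

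The final paragraph, dated 12-8-2019, explains why: "We excluded the baseline VISA-A score as adjusted variable in the GEE-model". The reason given is that "adjustments are already being made as the baseline VISA-A score is included in the model as time point", and the conclusion, attributed to the trial's statisticians, is that "it was not necessary to adjust for this variable twice".

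The SAP does not state the group and time terms, whether the arms share a baseline mean, the working correlation, or which contrast is the primary comparison. The first paragraph also extends the GEE beyond VISA-A ("The same approach will be used for the following secondary outcomes", followed by six outcomes), but the update speaks of VISA-A alone.

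**The concern.** The update treats two different things as the same. Covariate adjustment subtracts from the follow-up difference the chance baseline difference multiplied by the regression slope of follow-up on baseline. Entering baseline as one more repeated outcome subtracts it with a weight set by the model terms and the working correlation. That weight may be zero, one, or something in between.

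This is the primary analysis. An analyst who accepts the rationale would regard baseline as dealt with when the adjustment may be absent or wrongly weighted. The price would be a wider confidence interval from data already collected, and an estimate that moves with chance baseline imbalance, in opposite directions for a visit contrast and a change contrast.

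**Working it through.** The SAP gives no sample size, SD, correlation or power, so there is no stated figure to reproduce. The check compares variances.

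**Inputs, all assumed.** r is the correlation between baseline and the follow-up visit given the retained covariates: 0.3, 0.5, 0.7. s is follow-up SD divided by baseline SD: 1 unless stated. Allocation is 1:1 and data are complete.

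**Form of the estimate.** For a visit, change or common-baseline contrast, the estimate is D_t − w·D_0, where D_t and D_0 are the arm differences at follow-up and baseline.

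- Arm-specific baseline means, group difference at a visit: w = 0.
- Arm-specific baseline means, group × time contrast: w = 1, whatever the working correlation.
- Common baseline mean, one common variance: w is the working correlation between baseline and that visit, hence 0 under independence.
- Analysis of covariance (ANCOVA): w = r·s, the regression slope, which has the smallest variance.

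**Variance relative to ANCOVA:** (s² − 2wrs + w²) / [s²(1 − r²)].

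With s = 1, w = 0 gives 1/(1 − r²), and w = 1 gives 2(1 − r)/(1 − r²) = 2/(1 + r).

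| | r = 0.3 | r = 0.5 | r = 0.7 |
|---|---|---|---|
| Visit contrast (w = 0) | 1/0.91 = 1.10 | 1/0.75 = 1.33 | 1/0.51 = 1.96 |
| CI wider by (square root) | 5% | 15% | 40% |
| Equivalent loss of patients (1 − 1/ratio) | 9% | 25% | 49% |
| Change contrast (w = 1) | 2/1.3 = 1.54 | 2/1.5 = 1.33 | 2/1.7 = 1.18 |
| CI wider by | 24% | 15% | 8% |
| Equivalent loss of patients | 35% | 25% | 15% |

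**Larger follow-up SD (s = 1.5).** The change ratio is (3.25 − 3r)/[2.25(1 − r²)]: 2.35/2.0475 = 1.15, 1.75/1.6875 = 1.04, 1.15/1.1475 = 1.00. The visit ratios do not change.

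**Common baseline mean with a poorly fitting working correlation (s = 1).** Suppose four follow-ups, a true correlation of 0.3 with baseline and 0.8 between follow-ups. An exchangeable structure averages to (4 × 0.3 + 6 × 0.8)/10 = 0.6. The ratio is (1 − 0.36 + 0.36)/0.91 = 1.10, the same as no adjustment. For AR(1) with parameter 0.5 at lag 4, w = 0.0625; with true r = 0.5 the ratio is (1 − 0.0625 + 0.0039)/0.75 = 1.26. If the working correlation equals r, the ratio is 1.00.

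**Chance imbalance.** If the treated arm starts 0.2 SD higher, the estimate differs from ANCOVA by (r − w) × 0.2. For r = 0.3, 0.5, 0.7 that is +0.06, +0.10, +0.14 SD (visit) and −0.14, −0.10, −0.06 SD (change).

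**Simulation check.** With an assumed 80 patients, four follow-ups and 1,500 runs per scenario, every visit, change and common-baseline contrast averaged 0.49 to 0.51 for a true effect of 0.50. A post-baseline GEE with baseline as covariate had variance 0.99 to 1.01 times ANCOVA in all seven scenarios.

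**A different tested term.** The form above does not cover a single treatment main effect pooled over all time points including baseline. There is no effect at baseline, so with k follow-ups a constant effect is estimated as k/(k + 1) of its size: 0.50, 0.75 or 0.80 for k = 1, 3 or 4.

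**The case against.** The strongest reply is that the update's decision is sound and only its reason is loosely worded. Baseline should not be both a repeated outcome and a covariate in one model, so dropping one role is defensible. A group × time contrast does account for baseline, with a fixed weight of one. A common-baseline model with a fitting working correlation reaches ANCOVA precision. The SAP does not say which model is meant, and an unseen protocol may. All of this stands, and it means a loss is possible rather than demonstrated. It does not rescue the rationale: being a time point is not what produces adjustment, and in most of the standard forms the result is not covariate adjustment.

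The weights also need complete data. With one follow-up, 20% missing completely at random and r = 0.7, the change ratio is 1.33 under independence and 1.14 under a correct exchangeable structure, against 1.18 with complete data. The SAP plans no imputation, so the table is a guide only.

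A reader might infer three stronger things that the document does not support.

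- That the primary comparison is biased. The visit, change and common-baseline contrasts are unbiased under randomisation. Dilution arises only with a pooled main effect, and the SAP does not say that this is the tested term.
- That the trial loses a particular share of its information. Neither r nor the model is given.
- That the covariate should go back into the present model. That would create the double use the update rightly avoids.

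**Conclusion.** The point holds, and should be fixed. The update's inference is wrong as stated: inclusion as a time point is not equivalent to covariate adjustment. The algebra is secure; the practical size is not known. Under equal SDs, complete data and r between 0.3 and 0.7, the variance penalty runs from 10% to 96% for a visit contrast and from 18% to 54% for a change contrast. It is close to nil for a change contrast with high r and a larger follow-up SD, or for a well-specified common-baseline model. The harm is lost precision and dependence on chance baseline imbalance, with dilution of the effect only if a main effect pooled over baseline were tested.

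**What to change.** Preferred: use only post-baseline VISA-A as the outcome. Include baseline VISA-A as a covariate beside the four already listed, with group, time and group × time, and test the adjusted group difference at the primary time point. A baseline × time term is optional and makes the result match visit-specific ANCOVA.

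Acceptable alternative: keep baseline as a time point, constrain the arms to a common baseline mean, place group × time terms at follow-up only, and use an unstructured working correlation. If SDs change over time this loses some precision, by an amount that depends on how the software scales the variance. At s = 1.5 and r = 0.3, 0.5, 0.7 the cost is 1%, 4%, 11% if w = r. It is 2%, 8%, 24% if one pooled variance is used with four follow-ups, because then w = r × 1.5/[(1 + 4 × 2.25)/5] = 0.75r.

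In either case, replace the update's rationale with a dated statement of the chosen model, and say whether it also applies to the six secondary outcomes analysed by GEE.

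The cost is SAP wording and one model statement. Baseline VISA-A is already collected, and the update implies that it was previously an adjustment variable. The preferred model uses one degree of freedom, or one per follow-up visit with baseline × time. Its real drawback is that patients with no post-baseline score contribute no outcome row, which sits awkwardly with the intention-to-treat principle; the alternative keeps them.
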